5.0 DATA COLLECTION AND MANAGEMENT

5.1 Registration Process

- Potential patient identified
- Patient signs informed consent and HIPAA form
- Eligibility Screening
- Register the patient on the study (Oncore)
- Assign a patient study number
- Pend blood work orders
- Documentation of Consent in EPIC

5.2 Electronic Data Capture

5.2.1 IPad Survey Administration

All of our study assessments are either self-administered or done by the CRC during regularly scheduled clinic visits whether in-person or virtual. In the case a patient does not have a monthly visit scheduled, the surveys will be administered over the phone or by use of a survey email link [APPENDIX N]. All assessments in survey form are completed via IPad and compatible pen with the exception that the CRC will administer the SPPB. Patients unable or unwilling to use the IPad will be offered a paper copy as an alternative to the electronic version.

5.2.2 Survey Software and Data Management

All data obtained via the IPad survey platform is supported by REDCap. The Ohio State University (OSU) Research Informatics Services (RIS) core utilizes REDCap as its primary Electronic Data Capture (EDC) support. The REDCap platform is a secure, web-based application flexible enough to be used for a variety of types of research, provides an intuitive interface for users to enter data, and enforces real time validation rules (with automated data type and range checks) at the time of entry.

REDCap data collection projects rely on a study-specific data dictionary defined in an iterative self-documenting process. The project specific data dictionary is defined by the research team with assistance from RIS staff. As part of the data dictionary development process, individual fields can be denoted as identifiers. When exporting a de-identified dataset, these variables are omitted. Additionally, the data export tool allows for the shifting/removal of dates. REDCap supports electronic signatures by positively identifying the user through a unique username and password combination. The provisioning of authorization (e.g. access to specific projects, user rights within the project, etc.) for all projects is managed by RIS staff in conjunction with the project Primary Investigator (PI).

5.2.3 DATA AND SAFETY MONITORING PLAN

Though this is not a clinical trial per the NIH definition, we have developed a Data and Safety Monitoring Plan for this project. The purpose of the data and safety monitoring plan is to ensure the safety of participants, the validity and integrity of data, and the appropriate termination of projects for which significant benefits or risks have been uncovered or when it appears that the project cannot be concluded

successfully. Risks associated with participation in research must be minimized to the extent practical, and the method and degree of monitoring should be commensurate with risk. The essential elements of the Data and Safety Monitoring Plan include:

- Monitoring the progress of the project and the safety of participants;
- Plans for assuring compliance with requirements regarding the reporting of adverse events (AE);
- Plans for assuring that any action resulting in a temporary or permanent suspension of the project is reported to the appropriate agencies; and
- Plans for assuring data accuracy and protocol compliance. Prior to the initiation of the project, staff will receive standardized training to ensure that the activities of the project are conducted in a uniform, safe, confidential and secure manner. A tracking system will be implemented to document data collection activities, and reports will be generated on a weekly and monthly basis to monitor the project activities. Research project meetings will take place on a monthly basis to monitor the activities of the project and to continually reassess the progress of the project, including assessments of data quality, timeliness, participant recruitment, accrual, retention and monitoring of the risks versus benefits throughout the project period. In addition, face-to-face meetings with project staff will take place once per week to discuss the project activities.

We will use REDCap (Research Electronic Data Capture) electronic data capture tools hosted by the Center for Clinical and Translational Science (CCTS) at OSU for data collection. REDCap provides a secure, web-based, HIPAA compliant application that is housed behind the OSU Medical Center firewall. This platform provides an intuitive data manipulation interface, custom reporting capabilities, audit trail functionality, and real-time data monitoring/querying of participant records. REDCap has multiple data export options to common statistical packages (SPSS, SAS, Stata, R/S-Plus).

To monitor data quality, the clinical research coordinator will conduct a 10% project eligibility verification. If a violation is noted, the clinical research coordinator will document the violation and inform the research project and the PI the matter. The appropriate action will be taken to rectify the violation and to determine what, or if any, corrective actions need to take place. All protocol violations will be documented and reported to the appropriate IRBs. Also, any privacy violations will be reported to the IRBs and the institutional privacy offices. All privacy violations, AEs, and protocol violations will be reported to and reviewed by the PI and the research team, who will be responsible for reporting to the OSU Office of Responsible Research Practices/IRB.

The clinical research coordinator will be responsible for submitting reports; annual reports will be sent to the OSU IRB, External Advisory Board, and, as required, to the OSUCC Data and Safety Monitoring Board and the NIA project office. Information included in the reports will include the number of individuals enrolled in the project, dropout rates and any protocol deviations.

Any unexpected SAE will be reported to the NIA, DSMC, and IRB within 48 hours of occurrence, while any other SAEs, protocol deviations, and anticipated problems will be made note to file and reported to the NIA, DSMC, and IRB within 72 hours. Any expected AE such as chemotherapy toxicity will not be reported but made note to file and documented within our REDCap database. The DSMC reviews safety reports every 6 months while all SAE reports are reviewed monthly. All submissions are made via OnCore. The PI will also submit a progress report (biannually for Phase II and quarterly for Phase I) that will be reviewed by the committee per the IRB of record as per the policies of the IRB.

5.3 Baseline Demographic Questionnaire

Patient demographic information will be collected via a standard form [APPENDIX O] administered at baseline. The information will be pulled from the patient demographics section in IHIS.

5.4 Clinical Data

Clinical data regarding the specifics of the patients thoracic malignancy will be collected from IHIS including but not limited to, diagnosis, diagnosis date, stage, genetic mutation information, prognostic measures, treatment history, medications, hospitalizations, readmissions, hematologic and chemistry parameters (e.g. creatinine, BUN, albumin).

6.0 STATISTICAL ANALYSIS

6.1 Primary Endpoint

In order to evaluate the feasibility of the pilot intervention we will determine, recruitment, adherence, and retention rates at 12-weeks of follow-up. Follow-up will continue through 24 weeks post-enrollment. Recruitment rates will be defined as the proportion of screened older adults accrued relative to those approached in the OSUCCC Thoracic Oncology Clinic.

Successful recruitment rates will be defined as $\geq 50\%$ of older adults (≥ 60 years) approached agree to participate. Study adherence will be defined as the completion of $\geq 70\%$ of the program sessions, repeated assessments, and collection of bio specimens either at the end of the study period or death, whichever occurs first. Retention rates will be defined as the percentage of participants not lost to follow-up at 6, 12, and 24 weeks post-enrollment. Death during active follow-up will not be considered as lost to follow-up. We are excluding those people who die because our population of interest is those who live long enough to benefit from this intervention. We will enroll 30 participants to account for a conservative drop out of 30% for a projected sample size of 20 participants who survive a 6 – month period. Reasons for missing any scheduled collection dates will be documented, and the proportions of missing information at each time point will be calculated.

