1.2 Hypothesis

We hypothesize that we will be able to accrue 20 older adults (≥ 60 years) with a thoracic malignancy and implement a 12-week virtual health-assisted physical activity + relaxation intervention program with biospecimen collection. We hope to achieve 70% adherence to all sessions and a total patient retention rate of 60% at the end of the 12 – week intervention program.

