3.3 Inclusion Criteria

- Age ≥ 60
- Diagnosed with advanced lung cancer: unresectable stage IIIA, IIIB, or stage IV NSCLC or extensive stage SCLC
- Intent to receive treatment from the OSUCCC Thoracic Oncology Clinic
- Patients are eligible at any time point during their treatment here at OSU. Rationale for this timeframe is due to the overwhelming nature of the first few visits and uncertainty

around an eventual treatment plan. Patients at any stage of their treatment can participate and benefit from a physical therapy and psychosocial intervention. Patients will be approached at their initial visit but we can also offer enrollment at any one of the patients regularly scheduled clinic visits. .

- Ability to understand and willingness to sign an informed consent document (or indicate approval or disapproval by another means).

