4.12 Biomarkers

Peripheral blood and stool samples will be collected at baseline prior to treatment and pre and post PT + PMR session. Thereafter, blood will be collected every 6 weeks pre and post PT + PMR session and at additional triggered time points for correlative biomarker studies. Each patient will have a minimum of 6 research blood draws performed (2 pre-treatment) and 4 total post-treatment. The post-PT +PMR blood sample will be drawn from the peripheral IV so an additional needle stick is not required. The blood will be processed into peripheral blood T lymphocytes (PBTLs), plasma, and serum for cellular senescence correlative analyses. The analysis consists of routine laboratory values including hematologic functions, renal function, hepatic function and calculated creatinine clearance, and markers of inflammation and coagulation, and potential molecular markers of aging (P16^{INK4a} Expression, DNAge). The details of this biological assessment are below:

Table 2: Biomarker Assessment

Laboratory Values captured in Routine Practice	Biologic Correlates*
Hematologic functions: WBC HGB Platelets Absolute Neutrophil count Absolute Lymphocyte count Absolute Lymphocyte count	Molecular markers of aging: OSU_Senescence DNAge Inflammatory Cytokines Peripheral blood T Lymphocyte subtyping
Renal Function: BUN Creatinine	
Hepatic function: AST ALT Total Bilirubin Alkaline Phosphatase Albumin	

*patients who have already begun treatment prior to visit 1 will not partake in research blood samples in order to preserve the integrity of the data.

Stool samples will be used for microbiome correlative analyses. At their clinic visit patients will be given a home microbiome collection kit that includes instructions for collecting a sample within 24 hours of their next clinic visit. (Please see **APPENDIX L** for the instructions included in this box.) Briefly, a rigid plastic scaffold is placed over the toilet seat to collect stool in a plastic tub. Patients return the sample at their next clinic. Staff transfer the samples to the [name] lab (IBC 2018R00000115) where stool is transferred to cryo-vials and stored at -80C until processing in batch.

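### Section 6.1 measures adherence by an unscored composite of sessions, assessments and specimens, which can misstate the session adherence that 1.2 sets at 70%

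*Combined protocol and SAP*

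**What the plan says.** The hypothesis in 1.2 ties the 70% figure to sessions: "We hope to achieve 70% adherence to all sessions". Section 6.1 names adherence as one of three primary feasibility measures, beside recruitment and retention, and defines it more widely: "Study adherence will be defined as the completion of $\geq 70\%$ of the program sessions, repeated assessments, and collection of bio specimens". It is scored at the end of the study period or at death, if earlier. Section 6.1 gives no weights, no rule for combining the three components, and no rule for items a patient is not permitted to complete.

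Three other statements bear on the specimen component:

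- Section 3.3: "Patients are eligible at any time point during their treatment here at OSU".
- Section 4.12, footnote to Table 2: "patients who have already begun treatment prior to visit 1 will not partake in research blood samples". The footnote names blood and does not mention stool.
- Section 4.12, main text: "Each patient will have a minimum of 6 research blood draws performed".

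Section 6.2.1 also uses the word adherence, but for patients continuing at 12 weeks (13 of 20). It adds that adherence for PT and for PMR will be determined at 24 weeks.

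**The concern.** Whether older patients with advanced lung cancer can keep up weekly PT and PMR is the central feasibility question. A patient's adherence status should therefore follow attendance. Under the 6.1 composite it can depend instead on two other things: whether treatment had begun before visit 1, which decides whether research blood may be given at all, and how many questionnaires and specimens are available to offset missed sessions. Because the scoring rule is unstated, two analysts with the same data could report different adherence rates, and neither rate need describe attendance. A larger trial planned from this figure could start from the wrong expectation.

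**Working it through.** **The plan's own figures.** The plan gives no sample size, power or cohort-level threshold for the composite. Its one calculation (6.2.1) concerns the follow-up rate: 40% against 64%, one-sided 10% error, 80% power. The normal approximation gives N = [(1.2816 × √0.24 + 0.8416 × √0.2304) / 0.24]² = 18.5, so 19, close to the stated 20. That calculation does not involve adherence as defined in 6.1, so the check below is direct counting.

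**Inputs**

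- Sessions: 12 weekly PT visits (4.2). PMR is taught at week 1 with weekly check-ins (4.3). The base count treats each week as one session; counting PMR separately gives 24 (assumption).
- Assessments: 4 full batteries (table in 4.3), or 6 if weeks 4 and 10 in the study calendar also count.
- Blood draws: at least 6 (4.12), or 8 if drawn before and after the session at all four biomarker visits (assumption).
- Stool: 4, one per biomarker visit in the calendar (assumption). If the 6 draws are read as three pre/post pairs, the matching stool count is 3.
- Share already on treatment at entry: not given.

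**Reading A: each component must reach 70%, barred draws stay in the denominator.** A barred patient who gives every stool sample completes stool / (draws + stool) of the specimens:

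- 4/(6 + 4) = 40%
- 4/(8 + 4) = 33%
- 3/(6 + 3) = 33%

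All fall below 70%, so this patient is non-adherent even at 12/12 sessions. If k of 20 patients are barred, the adherence rate cannot exceed (20 − k)/20. For illustration only, k = 5 caps it at 75% and k = 10 at 50%. Under this reading a poor attender cannot pass, because the session component must itself reach 70%.

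**Reading B: components pooled.** The base count is 12 + 4 + 6 + 4 = 26 items. A patient who completes everything except some sessions has s + 14 items. Four sessions give 18/26 = 69.2% (fails). Five give 19/26 = 73.1% (passes), at 5/12 = 42% attendance. If a barred patient's draws are removed, the total is 20 items, and 6 sessions give (6 + 4 + 4)/20 = 70% (passes).

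| Sessions + assessments + draws + stool | Fewest sessions that pass, blood given | Fewest sessions that pass, barred draws removed | Barred full attender, all stool, draws kept |
|---|---|---|---|
| 12 + 4 + 6 + 4 = 26 | 5 (42%) | 6 (50%) | 20/26 = 77% |
| 12 + 6 + 8 + 4 = 30 | 3 (25%) | 6 (50%) | 22/30 = 73% |
| 24 + 4 + 6 + 4 = 38 | 13 (54%) | 15 (63%) | 32/38 = 84% |
| 24 + 6 + 6 + 4 = 40 | 12 (50%) | 14 (58%) | 34/40 = 85% |

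The last column shows that pooling does not generally fail barred full attenders. It does so only in the smaller counts when stool is also missed: on 26 items with 2 of 4 stools, (12 + 4 + 2)/26 = 69.2%. With 24 sessions and no stool at all, such a patient still scores 28/38 = 74% or 30/40 = 75%.

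**Sessions only.** 8/12 = 66.7% and 9/12 = 75%, so 9 of 12 is the smallest passing count. For 24 contacts, 16/24 = 66.7% and 17/24 = 70.8%, so 17 of 24.

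**The case against.** Four points can be made for the plan.

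- **Barred draws may never have been meant to count.** The footnote says these patients take no part in research blood, so one natural reading is that no draw is scheduled and none is missed. That would remove the Reading A problem. But the main text of 4.12 promises at least 6 draws for every patient, and 6.1 does not settle the matter. Removing the draws also leaves the pooling problem in place.
- **Specimen collection belongs to the feasibility question.** This stands: 1.2 hypothesizes a program delivered with biospecimen collection. A reader might infer that the composite has nothing to do with the hypothesis; the documents do not support that. The 70% figure in 1.2 is nevertheless attached to sessions.
- **Other reporting helps.** Section 6.1 promises reasons for missed collections and proportions missing at each time point, and 6.2.1 promises PT and PMR adherence. The latter is at 24 weeks, not the 12-week primary time point, and has no definition of its own.
- **The decision rule is untouched.** This stands. The 13-of-20 rule is applied to patients continuing at 12 weeks, although 6.2.1 labels the result adherence.

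A reader might also infer that the blood bar makes fully attending patients fail and poor attenders pass at the same time. The documents do not support that as a general statement. The first error comes mainly from per-component scoring with barred draws retained. The second comes from pooling and has nothing to do with the bar. Both can occur under one rule only in particular counts, such as 26 pooled items with half the stool missed.

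**Conclusion.** The concern holds as a defect in the definition of a primary feasibility measure. Section 6.1 does not measure the session adherence targeted in 1.2, and its unstated scoring rule matters. Scored per component with barred draws counted, an eligible patient already on treatment is non-adherent at full attendance, with at most about 33-40% of specimens. Pooled, a patient who completes everything else is adherent with 5 of 12 sessions on 26 items (3 to 5 of 12, or 12 to 13 of 24, across the counts tabulated). Excluding barred draws does not cure the pooling error.

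These figures rest on the assumed stool, session and assessment counts. A downward bias of a particular size cannot be claimed, because the already-treated share is not given and the bias depends on barred draws being counted. The consequence is a potentially misleading adherence rate, not a wrong decision under the continuation rule. The plan should be amended before adherence is scored.

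**What to change.** In 6.1, define primary adherence as completion of at least 70% of the supervised sessions scheduled up to the end of the intervention or death, whichever is earlier. That is 9 of 12 for a patient with all 12 scheduled, or 17 of 24 if PT and PMR contacts are counted separately; state which count applies. Give the overall figure, as in 1.2, and also show PT and PMR. Keeping the death cutoff matters: a fixed 9 of 12 would score early deaths as non-adherent, which 6.1 does not intend.

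Report assessment completion and specimen completion as separate feasibility rates, with the blood denominator limited to patients whom 4.12 allows to give research blood.

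The cost is a change of wording in 6.1 and two more rows in the feasibility table. No new data, visits or patients are needed. The headline adherence figure may come out higher or lower than under the composite.

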1.1 Primary Objective

To assess the feasibility of a novel, weekly supervised virtual health-assisted physical therapy plus relaxation intervention delivered to older adults with advanced thoracic malignancy (N=20). The overall goal is to be able to pilot this intervention targeting modifiable risk factors for worsening functional status: physical performance and negative mood.

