3.0 METHODS

3.1 Study Overview

This is a prospective, longitudinal study of 20 adults ≥ 60 years of age with advanced thoracic malignancy (NSCLC or SCLC) who plan to receive either immunotherapy and or chemotherapy treatment from the OSUCCC Thoracic Oncology clinic. This cohort is a 12-week pilot intervention consisting of a physical therapy and progressive muscle relaxation program delivered to older adults with advanced lung cancer. Functional trajectories and resiliency will be characterized in this cohort. Enrolled patients will participate in in-person physical therapy and progressive muscle relaxation sessions that are incorporated into routine treatment visits as well as performed via virtual health on the non-treatment weeks. Patients’ functional status will be assessed every 3 weeks and clinical outcomes will be evaluated every 6 weeks. Correlative biomarkers will also be assessed through blood and stool sample collection. Patient follow up will continue through 24 months post enrollment for 1 year and 2 year overall survival.

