4.0 STUDY DESIGN

4.1 Overview of Study Design

This is a prospective longitudinal study of 20 adults older than 60 years who have been diagnosed with a thoracic malignancy who intend to receive treatment at the Ohio State University. Eligible participants will undergo the informed consent process. With IRB and participant permission, demographic information will be collected on potential participants who decline enrollment in the study by use of a non-enrollment survey [Appendix A].

[figure not shown]
Participants will undergo treatment prescribed by the treating physician as per standard of care. In addition, patients will undergo an in-person and virtual health physical therapy program. The

in-person program will include a 10-minute cardiovascular warm up on a portable exercise peddler, using either their upper or lower extremities depending on patient abilities. The warm up will be followed by a resistance training module using exercise resistance bands. This is designed to strengthen the core and upper/lower extremities. The workout will end with full body stretches that are held for 30 seconds each. The virtual health visits will include the exact same regimen and equipment as the in-person visits. The portable peddler and resistance bands will be given to the patients either in clinic or mailed to their home based on patient preference.

In addition to the physical therapy program, participants will undergo progressive muscle relaxation (PMR) performed by research graduate students (MA and PhD level) in clinical psychology. The patient is taught to systematically tense and release 16 different muscle groups. Patients will be seen during their regularly scheduled clinic visits and with virtual health “check-ins” in the off-treatment weeks.

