4.14 Disease Response

Disease response will be routinely evaluated and will be classified using RECIST 1.1 criteria.⁴¹ The current version of RECIST is the most widely used tumor response criteria used in clinical trials. RECIST categorizes disease as either measurable or non-measurable. The disease response is then classified into the following categories; complete response (CR), partial response (PR), non-CR/non-PR, and Progressive disease (PD).⁴² The study clinician will evaluate individual disease response for all 20 study participants. The CRC will be notified of any PD as this will require triggered study assessments.

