6.2.1 Power Calculations

A follow-up rate of study participation at 12 weeks of at least 60% (p_1) would be desirable; a continuation rate below 40% (p_0) would be unacceptable. With 20 eligible and recruited participants alive during a 24 week follow-up period, this study is powered to reject acceptability of these measures if the follow-up rate is less than 40% (10% one-sided type one error) and deemed feasible if the follow-up rate is 64% or more (80% power). If 13 of the 20 patients continue at 12 weeks, we will consider this method to have acceptable adherence for further study (follow-up rate >40%). We will also determine adherence and follow-up rates for both PT and PMR at 24 weeks of follow-up.

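### Sections 1, 3 and 4 describe a study of 20 patients, section 6.1 enrols 30 to leave 20, and the 13-of-20 decision rule has no cut-off for any other evaluable number

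*Combined protocol and SAP*

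**What the plan says.** Five places outside the statistical section give the study size as 20:

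- Section 1.1: "delivered to older adults with advanced thoracic malignancy (N=20".
- Section 1.2: "we will be able to accrue 20 older adults", with "a total patient retention rate of 60% at the end of the 12" weeks.
- Section 3.1: "This is a prospective, longitudinal study of 20 adults".
- Section 4.1: "This is a prospective longitudinal study of 20 adults older than 60 years".
- Section 4.14: the clinician will "evaluate individual disease response for all 20 study participants".

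Section 6.1 gives a different enrolment number: "We will enroll 30 participants to account for a conservative drop out of 30% for a projected sample size of 20 participants". Those 20 are described as six-month survivors. The same section does not count a death during active follow-up as loss to follow-up.

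Section 6.2.1 takes as its denominator 20 eligible, recruited participants alive during 24 weeks. It sets an unacceptable rate of 40%, a one-sided type I error of 10% and 80% power at 64%. The decision rule reads "If 13 of the 20 patients continue at 12 weeks", in which case adherence is judged acceptable for further study.

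**The concern.** Section 1.2 uses the verb for enrolment with 20, and section 6.1 uses it with 30. The figure of 30 appears only in section 6.1. A team working from sections 1 to 4 would close accrual at 20, and a team working from section 6.1 would close at 30.

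The feasibility decision is a fixed count out of 20, and that 20 is a projection from 30 enrolled. The number alive over 24 weeks will vary, and the plan gives no cut-off for any number but 20. The conflict therefore affects both when accrual stops and whether the decision rule can be read at the end.

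**Working it through.** **Inputs.** Enrolment of 20 (1.1, 1.2, 3.1, 4.1, 4.14) or 30 (6.1); loss of 30% and projected sample of 20 (6.1); unacceptable rate 40%, one-sided error 10%, rate for power 64%, rule 13 of 20 (6.2.1).

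**Step 1: the plan's own enrolment figure.** Required enrolment = 20 / (1 − 0.30) = 28.6, rounded up to 29. Forward, 30 × 0.70 = 21. The stated 30 is reproduced, with one patient of upward rounding. Going from 30 to exactly 20 is a loss of 1 − 20/30 = 33%, a trivial difference.

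**Step 2: accrual stops at 20.** Expected evaluable = 20 × 0.70 = 14. If the count of 13 is kept, P(X ≥ 13 | n = 14, p = 0.64) = 0.017, about 0.02. An intervention with the rate the plan wants to detect would almost never pass.

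**Step 3: 30 are enrolled.** Treat the number evaluable as Binomial(30, 0.70).

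- P(exactly 20) = 0.14
- P(at least 20) = 0.73
- P(at least 24) = 0.16

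So a denominator other than 20 is the usual outcome even when section 6.1 is followed exactly.

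**Step 4: a fixed count of 13 as the denominator moves.** Type I error = P(X ≥ 13 | n, p = 0.40):

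| Evaluable n | Type I error of 13 |
|---|---|
| 20 | 0.021 |
| 21 | 0.035 |
| 23 | 0.081 |
| 24 | 0.114 |
| 30 | 0.42 |

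The 10% limit is passed from 24 upward.

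**Step 5: cut-offs that hold the stated error.** The smallest r with P(X ≥ r | n, 0.40) ≤ 0.10, with power at 64%:

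| n | r | Type I error | Power at 64% |
|---|---|---|---|
| 14 | 9 | 0.058 | 0.61 |
| 18 | 11 | 0.058 | 0.70 |
| 20 | 12 | 0.057 | 0.73 |
| 21 | 12 | 0.085 | 0.81 |
| 23 | 13 | 0.081 | 0.83 |
| 25 | 14 | 0.078 | 0.85 |
| 30 | 16 | 0.097 | 0.92 |

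**The case against.** The strongest reply is that sections 6.1 and 6.2.1 agree with each other: 30 enrolled, 20 evaluable, 13 of those 20. The other mentions of 20 could then mean the target analysed cohort. That reading is available for sections 1.1, 3.1, 4.1 and 4.14. It does not fit section 1.2, where accruing 20 is itself the hypothesis, and it leaves the rule without a cut-off when the number alive is not 20.

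The reply does stand against several stronger readings that a reader might infer:

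- **That the drop-out arithmetic fails.** It does not: 30 is ordinary upward rounding of 28.6.
- **That the rule has no defined sample.** Section 6.2.1 names one. The difficulty is that it is a projected, random number, resting on survival to 24 weeks while the rule is read at 12.
- **That the 60% retention target means a 40% shrinkage of the evaluable set.** The plan's retention rate treats a living patient who stops as a failure inside the denominator, so this target does not reduce the denominator.
- **That stopping at 20 is what costs the stated 80% power.** At the full 20 evaluable, 13 of 20 has exact power of only 0.56 at 64%, below the 0.61 of 9 of 14. The gap from 80% is a separate matter and cannot be put down to accrual.
- **That the plan runs a 42% type I error.** That figure arises only if 13 is counted against 30 evaluable patients. Section 6.2.1 says 13 of 20, so this is the far end of a range and not the plan's own rule.

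**Conclusion.** The point holds. The enrolment number is contradictory (20 against 30), and the feasibility rule is specified for a single evaluable number that is unlikely to occur exactly. With accrual stopped at 20 and 30% loss, about 14 are evaluable and 13 is nearly unreachable (probability about 0.02 at a 64% rate). With 30 enrolled, exactly 20 evaluable has probability about 0.14, and a fixed 13 breaches the 10% error from 24 evaluable upward.

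These figures assume independent patients and a 30% chance of leaving the evaluable set. They also take that 30% to be removal from the denominator. Section 6.1 says drop out, while the surrounding text on survival suggests death, so this reading is an inference. The documents do not show which enrolment figure is the operative ceiling. This should be corrected before the rule is used.

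**What to change.** 1. Reconcile sections 1.1, 1.2, 3.1, 4.1, 4.14 and 6.1 to one enrolment figure, and distinguish enrolled from expected evaluable wherever a sample size appears. If 30 is intended, state 30 enrolled and about 20 to 21 expected evaluable in sections 1, 3 and 4. If 20 is the ceiling, restate the expected evaluable number (about 14) in sections 6.1 and 6.2.1, with the rule and power that follow.
2. Say in section 6.1 whether the 30% covers death, withdrawal or both. Keep living patients who stop participating in the denominator as failures.
3. In section 6.2.1, state that 13 of 20 applies to the defined evaluable set only. Add the exact-binomial cut-off for each possible evaluable number, holding type I error at or below 10% at a 40% rate: for example 9/14, 11/18, 12/20, 12/21, 13/23, 14/25 and 16/30. If the stricter 13 is kept at 20, say that this is deliberate.

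The cost is text and one short table. If 30 is the intended figure, no patients are added beyond those section 6.1 already plans, though that is 10 more than sections 1 to 4 describe. If 20 is the ceiling, the cost is a smaller evaluable set and a restated power.
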